3.2.2. Subject Population Analyzed

The following analysis populations are defined for this study:

- Safety Set: All patients who are randomized and received at least 1 dose of ISIS 766720.
- Full Analysis Set (FAS): All randomized patients who received at least 1 dose of ISIS 766720- and have at least 1 post-baseline efficacy or PD assessment.
- Per Protocol Set (PPS): All FAS patients who complete at least 6 of the 8 doses of ISIS 766720 within the first 27 weeks administered and have no significant protocol deviations that would be expected to impact efficacy.
- PK Set: All randomized patients who receive at least 1 dose of ISIS 766720 and have at least one evaluable PK sample.

In addition to the above analysis sets, it is recognized that some data displays will be provided for "All Screened", "Screening Failures" and "All Randomized" subjects but no data analysis is planned to be executed in these populations.

Summary of related COVID-19 public health emergency incidence will be described in detail in the corresponding sections.

3.2.3. Handling of Missing Data

Missing values will not be imputed. Patients with missing data for a scheduled assessment time point were excluded from the summary for that time point.

Summary of missing visits for key study parameters will be summarized. Number of patients with missing data and missing data related to COVID-19 public health emergency may be provided.

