For other endpoints, baseline is defined as the last non-missing value prior to the first administration of ISIS 766720.

Analytical visits:

In general, all post-baseline data will be summarized using the visit labels provided in the data. Multiple results with the same visit label will be averaged for the continuous variables, and the worst result will be used for the categorical variables. Results with visit labels as “Unscheduled” will not be included in the by-visit summary tables and figures except for determining baseline and the incidence of abnormality lab summary including AST, ALT, platelet and renal but will be presented in data listings.

For patients who had last dose prior to treatment termination, PD results greater than 3 weeks after the last dose (the date of last dose + 21 days) up to treatment termination will not be included in the by-visit summary tables and figures. Also, for patients who started other acromegaly medications in the post-treatment period, PD results after the start date of acromegaly medication will not be included in the by-visit summary tables and figures.

Other situations, such as required additional confirmation, will be described separately in the related endpoint analysis approach.

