3.2.4. Disposition of Subjects

The number of patients screened, the number of patients screen failures, the number and percentage of patients enrolled, the number and percentage of patients completed the study treatment, the number and percentage of patients who discontinued from treatment early and reason, the number and percentage of patients completed post-treatment follow-up, and who discontinued from post-treatment follow-up and reason will be summarized.

A by-patient listing will also be provided.

Additional listing will be provided to describe the screen failure, treatment/post-treatment follow-up termination incidences related COVID-19 public health emergency.

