3.3.3. Sample Size Consideration

Approximately 40 patients are planned to be randomized in the study while considering an estimated 10% overall drop-out rate. Based on the assumption of expected IGF-1 reduction of 27.5% from Baseline with SD of 30% per treatment group, the minimum sample size of 12 evaluable patients per treatment group will provide 80% power to detect the difference between the null hypothesis of no change and the expected reduction using a 2-sided one-sample t-test with a significant level of 5%.

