3.3.5. Incomplete or Missing Data

In general, missing IGF-1 for a scheduled assessment will not be imputed. Patients with missing data for a scheduled assessment time point will be excluded from the summary for that time point.

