3.4. Secondary Analyses

3.4.1. Secondary Endpoint Definitions

Normalized IGF-1 level is defined as the ratio of the serum IGF-1 level and patient's upper limit of normal (ULN). The ULN will be varied among patients due to gender and age. Patients whose calculated ratios at scheduled visits are less than or equal to 1.2 or 1.0 will be deemed as achieving normalized IGF-1 at that scheduled visit.

For change from Baseline, non-missing IGF-1 measures over time will be compared to their baseline.

Patients without IGF-1 measure at a scheduled visit will not be imputed for that scheduled visit.

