3.4.2. Analysis of Secondary Endpoints

The analysis population will be conducted in both FAS and PPS. The results will be summarized by the ISIS 766720 dose received at randomization and overall. In addition, the results will also be summarized by the maximum ISIS 766720 dose received through the study and overall.

Subset analysis will be conducted among uncontrolled population ($IGF-1 > 1.3 \times ULN$ at Day 1) and high-strata IGF-1 population ($IGF-1 > 2.5 \times ULN$ at Screening), separately.

Proportion of subject incidence of achieving within 1.2 times, achieving 1.0 times of ULN over time will be summarized at each scheduled visit respectively. The estimated proportion with 95% confidence interval will be provided.

Absolute, change and percent change from Baseline to each scheduled post-baseline visit in IGF-1 over time will be summarized at each scheduled visit.

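### In the visible text, the Week 27 IGF-1 normalisation rates are observed-case in the FAS as well as the PPS, so early leavers drop out of the denominator; the likely effect is small and the remedy cheap

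*Combined protocol and SAP*

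**What the plan says.** Three SAP sections give the same missing-data rule.

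- Section 3.2.3, for all data: "Patients with missing data for a scheduled assessment time point were excluded from the summary for that time point".
- Section 3.3.5, for IGF-1: "Patients with missing data for a scheduled assessment time point will be excluded from the summary for that time point".
- Section 3.4.1, for the secondary endpoints: "Patients without IGF-1 measure at a scheduled visit will not be imputed for that scheduled visit". The same section defines a normalised patient only from a calculated IGF-1/ULN ratio and gives a missing ratio no category.

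On populations, section 3.4.2 states: "The analysis population will be conducted in both FAS and PPS". It reports the 1.2 and 1.0 times ULN proportions at each scheduled visit with a 95% confidence interval. Protocol 10.6.3 names an exact binomial test in both sets and gives no rule for missing values.

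Neither set requires a Week 27 value (SAP 3.2.2). The FAS needs one dose and one post-baseline efficacy or PD assessment. The PPS is described as "All FAS patients who complete at least 6 of the 8 doses of ISIS 766720 within the first 27 weeks administered", with no significant deviation expected to affect efficacy.

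SAP 3.2.1 also removes from the by-visit summaries, for patients whose last dose precedes treatment termination, "PD results greater than 3 weeks after the last dose (the date of last dose + 21 days) up to treatment termination".

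Losses are to be disclosed. Section 3.2.4 reports "the number and percentage of patients who discontinued from treatment early and reason", and section 3.2.3 plans a summary of missing visits for key parameters.

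**The concern.** Normalisation of IGF-1 is the trial's only secondary objective. There is no control arm, so each dose group's proportion is read on its own. An observed-case proportion describes patients still under observation on drug at Week 27, which is not the same group as those who began treatment. The FAS, which a reader would expect to show whether drop-out matters, applies the same exclusion and so cannot show it.

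The protocol Synopsis and section 8.8 have a patient who needs another acromegaly drug stop study drug and enter the Post-Treatment Period. If that happens before Week 27, an evident lack of response is handled as a missing value.

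**Working it through.** **The plan's own figures.** SAP 3.3.3 assumes a 27.5% reduction, SD 30%, two-sided alpha 5%, and 12 evaluable patients per group for 80% power. Exact noncentral-t power is 78.2% at n = 11 and 82.4% at n = 12, so 12 is the smallest n that reaches 80%. Three groups of 12 make 36, and 36/(1 − 0.10) = 40, the planned total. The visible text gives no expected rate or power for the normalisation endpoints.

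**Direction.** With x normalised, N patients in the set and m of them without an eligible Week 27 value, the plan reports x/(N − m). Counting the m as not normalised gives x/N. The first can never be below the second. The gap is the observed rate multiplied by the missing share m/N.

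**Size.** The SAP gives only an overall figure, "while considering an estimated 10% overall drop-out rate". The share missing at Week 27 must be assumed.

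- Constant drop-out rate from Day 1 to Day 505: 1 − 0.9^(182/504) = 0.0373, about 1.5 of 40 patients.
- Upper illustration: all 10% leave before Week 27, 4 of 40 patients.

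| Assumed observed rate | Gap at 3.73% missing | Gap at 10% missing |
|---|---|---|
| 30% | 1.1 points | 3 points |
| 50% | 1.9 points | 5 points |
| 70% | 2.6 points | 7 points |

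The ratio of the two rates is 1/(1 − 0.0373) = 1.04 in the first case and 1/0.9 = 1.11 in the second.

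**One group of planned size.** Suppose 6 of 12 observed patients normalise and one further patient has left (Clopper-Pearson intervals):

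- observed-case: 6/12 = 50.0% (95% CI 21.1 to 78.9, width 57.8 points);
- leaver counted: 6/13 = 46.2% (95% CI 19.2 to 74.9).

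The shift is 3.8 points.

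**What the 21-day rule adds.** From Appendix A, doses fall on Days 1, 15, 29, 57, 85, 113, 141 and 169 before the Week 27 visit on Day 183.

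| Last dose | Doses received | Days to Day 183 | Smallest gap within visit windows |
|---|---|---|---|
| Week 17, Day 113 | 6 | 70 | 176 − 120 = 56 |
| Week 21, Day 141 | 7 | 42 | 176 − 148 = 28 |
| Week 25, Day 169 | 8 | 14 | 0 (largest 28) |

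A patient last dosed at Week 17 or 21 can meet the PPS dose criterion and still have no eligible Week 27 value. A patient last dosed at Week 25 loses the value only if the gap stretches past 21 days. However, protocol 6.1.2 asks patients who stop to attend the early termination visit (ETTX) as soon as possible, preferably 4 weeks after the last dose. That is Day 113 + 28 = 141 or Day 141 + 28 = 169, both before Day 183. Most such patients would have left already, and the rule adds only the few who stop dosing yet still attend Week 27.

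**The mean and the primary test.** At the planned values with n = 12, t = −3.18 and p = 0.0088. Adding one leaver at zero change gives n = 13, mean −25.4, SD 29.7, t = −3.08 and p = 0.0095. The test hardly moves.

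**The case against.** The strongest reply is that this changes no conclusion. A shift of 1 to 3 points is slight beside an interval nearly 58 points wide. The larger figures need the whole overall drop-out to fall before Week 27, which the documents do not say. This stands, and it sets the priority.

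Loss for lack of effect before Week 27 is also limited by the protocol's own recommendations. The Synopsis advises waiting until after Week 17 before starting other acromegaly drugs. Section 8.7 advises holding an efficacy-adjusted dose for 3 months; from Day 113 that runs to about 113 + 91 = Day 204, after Day 183. Section 8.10.1 recommends being on a maximal dose first. The Appendix B footnote makes IGF-1 results routinely available only from Week 17 and then every three months, unless the investigator and medical monitor agree to more. This too stands, although stopping for symptoms or safety remains possible.

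A third reply is that a reader given the FAS size and the responder counts can work out the other rate. That is largely true, but the reported proportion and its interval remain the observed-case ones.

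Two stronger readings are tempting. One is that the 21-day rule strips many PPS patients from the denominator; the ETTX timing argues against it. The other is that the plan has no analysis counting leavers as not normalised. The public text cannot establish this, because SAP 3.5 (exploratory analyses) and protocol 10.6.5 (additional analyses) are absent from it.

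**Conclusion.** The point holds for the visible text. The Week 27 normalisation proportions are observed-case in both analysis sets, and they can only equal or exceed the rate that counts leavers as not normalised. The likely excess is about 1 to 3 points, or 3 to 7 points at the upper illustration. These sizes rest on assumptions: observed rates of 30% to 70%, and either a constant drop-out rate or all of the 10% falling before Week 27. The actual share missing at Week 27 is unknown.

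A reader might infer that the primary result is also compromised. The documents do not support that. The direction of any bias in the mean depends on why patients leave, and the test against zero barely changes. The priority is low: a cheap improvement to a one-directional feature of the secondary endpoint.

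**What to change.** In SAP 3.4.1 and 3.4.2:

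1. For the FAS Week 27 proportions at 1.2 and 1.0 times ULN, use all FAS patients as the denominator and count those without an eligible Week 27 IGF-1 as not normalised.
2. Keep the observed-case proportion as a sensitivity analysis.
3. Add a sensitivity analysis that uses any measured Week 27 value excluded by the 21-day rule, so that a measured normal value is not simply overridden.

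Leave the PPS primary analysis and the one-sample t-test unchanged. No added analysis of the mean is needed.

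The cost is SAP wording and a small amount of extra tabulation from data already collected. The downside is a slightly less favourable rate. Patients whose Week 27 value is missing for an unrelated reason, such as COVID-19 disruption, also count as not normalised, which is why the observed-case figure is kept. The FAS still omits any dosed patient with no post-baseline assessment, so the new rate comes close to, but does not fully cover, everyone who began treatment.

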3.2.4. Disposition of Subjects

The number of patients screened, the number of patients screen failures, the number and percentage of patients enrolled, the number and percentage of patients completed the study treatment, the number and percentage of patients who discontinued from treatment early and reason, the number and percentage of patients completed post-treatment follow-up, and who discontinued from post-treatment follow-up and reason will be summarized.

A by-patient listing will also be provided.

Additional listing will be provided to describe the screen failure, treatment/post-treatment follow-up termination incidences related COVID-19 public health emergency.

3.2.5. Demographic and Baseline Characteristics

Demographic and Baseline characteristics will be summarized using descriptive statistics by safety population. The summary includes age, gender, ethnicity, race, weight, height, and body mass index (BMI). Other disease characteristics related assessments, such as serum IGF-1, will be summarized in the summary tables separately.

For summarizing race, if multiple races are recorded in the database, then ‘Multiple Race’ is used in the summary table. The listing will display the specific race values.

BMI will be computed using the formula: $BMI = (\text{weight in kilograms}) / [\text{screening height in cm}/100]^2$

All protocol deviations will be listed and be summarized. Additional summary table by deviation type and classification will be provided to illustrate the protocol deviations related COVID-19 public health emergency.

3.2.6. Scoring of Questionnaires and Ring Size Assessment

Acromegaly Quality of Life Questionnaire (AcroQoL)

AcroQoL is a specific questionnaire designed to evaluate Health Related Quality of Life (HRQoL) in patients with acromegaly. It comprises 22 items ([Table 1](#)), which are spread across 2 dimensions: physical (8 items) and psychological (14 items). There is a further breakdown of the psychological dimension into 2 sub-dimensions (each comprising 7 items): one evaluates appearance and the other evaluates the impact of the disease on the patient’s personal relationships.

Table 1: The AcroQoL Questionnaire

Item
1 My legs are weak*
2 I feel ugly**
3 I get depressed*
4 I look awful in photographs**
5 I avoid going out very much with friends because of my appearance***
6 I try to avoid socializing***
7 I look different in the mirror**
8 I feel rejected by people because of my illness***
9 I have problems carrying out my usual activities*
10 People stare at me because of my appearance***
11 Some part of my body (nose, feet, hands,...) are too big**
12 I have problems doing things with my hands, for example, sewing or handling tools**
13 The illness affects my performance at work or in my usual tasks*
14 My joints ache*
15 I am usually tired*
16 I snore at night**
17 It is hard for me to articulate words due to the size of my tongue**
18 I have problems with sexual relationships***
19 I feel like a sick person*
20 The physical changes produced by my illness govern my life***
21 I have little sexual appetite***
22 I feel weak*

Frequency of occurrence (always, most of the time, sometimes, rarely, never) or degree of agreement with the items (completely agree, moderately agree, neither agree nor disagree, moderately disagree, completely disagree) are the response choices. * Scale 1 (Physical) ** Scale 2-1 (Psychological/ appearance) *** Scale 2-2 Psychological/ personal relations)

AcroQoL dimension	Questions included in each dimension
Physical	1, 3, 9, 13, 14, 15, 19, 22
Psychological	2, 4, 5, 6, 7, 8, 10, 11, 12, 16, 17, 18, 20, 21

Sub-dimensions (of the psychological dimension)	Questions included in each sub-dimension
Appearance	2, 4, 7, 11, 12, 16, 17
Personal relations	5, 6, 8, 10, 18, 20, 21

Each of the 22 items of the AcroQoL is answered in a 1 to 5 Likert scale measuring either the frequency of occurrence (always, most of the time, sometimes, rarely, or never) or the degree of agreement with the items (completely agree, moderately agree, neither agree nor disagree, moderately disagree, completely disagree). Answers to each of the items are rated on a scale of 1 to 5: 1 corresponds to the response category “Always” or “Completely agree”, depending on the item type, and 5 is equivalent to the response category “Never” or “Completely disagree”. This means that the lower the score the greater the impact on HRQoL.

The scores for each dimension or sub-dimension are the sum of the item responses given for each dimension / sub-dimension. Consequently, the score for the physical dimension can range from 8 to 40 points, the psychological dimension from 14 to 70 points, and each of the sub-dimensions (appearance and personal relationships) from 7 to 35 points. All these scores are interpreted by

taking the lowest score as corresponding to the worst imaginable HRQoL, and the highest score as corresponding to the best imaginable HRQoL, as expressed through the specific scales of this questionnaire. In addition, a global score can be calculated by the sum of the responses to the 22 items, which can range from 22 points (worst HRQoL) to 110 points (best HRQoL).

To simplify interpreting questionnaire scores, the raw scores can be standardized on a scale running from 0 (worst HRQoL) to 100 (best HRQoL), by using the following formula:

$$Y = \left[\frac{(X) - \text{min}}{(\text{max} - \text{min})} \right] \times 100$$

Here Y is the re-calculated score, and X is the sum of all the item responses within the dimension or global score (min. is the minimum possible score in the study dimension, and max. is the maximum possible score in the study dimension).

For example, to standardize the global score (Y), substitute X for the sum of the scores of the 22 items, min for 22 and max for 110 (being the two extreme values); thus, scores range from 0 (worst HRQoL) to 100 points (best HRQoL).

$$\text{Global score } Y = \left[\frac{(X) - 22}{(110 - 22)} \right] \times 100$$

To interpret each of the questionnaire scores, all of the items should be answered. However, for most HRQoL questionnaires a score is considered calculable if the percentage of un-answered questions does not exceed 25% of the items used to obtain the score. In such cases, one assumes that the scoring of the missing item or items is equivalent to the average score obtained in the rest of the items that make up the calculation of the score. In the case of AcroQoL, scores can be interpreted for each of the dimensions if the number of unanswered items does not exceed 2 in the physical dimension, 1 in the appearance and personal relationships sub-dimensions, or 3 in the psychological dimension. To get a global score, the maximum number of unanswered questions permissible is 5. The standardized scores of each dimension and global score will be tabulated.

Euro QoL-5 Dimensions (EQ-5D)

The EQ-5D is the most widely used generic PRO instrument internally ([Kind 2005](#)) and recommended by NICE for evidence submitted to its technology appraisal process ([NICE 2013](#)). The EQ-5D is comprised of 6 questions. The first 5 questions address the following quality of life dimensions: mobility, self-care, usual activities, pain/discomfort and anxiety /depression. The last question is represented by a 20-cm vertical visual analogue scale (VAS), scored from 0 to 100 asking the patient to “mark your own health state today” ([Brooks 1996](#)). A new version of the instrument, the five level EQ-5D was developed to improve sensitivity and to standardize the language used across dimensions ([Herdman et al. 2011](#)) and the study utilizes this latest instrument.

The EQ-5D comprises the same five questions/dimensions but increases the available response options ('levels') from three to five (no; slight; moderate; severe; extreme problems/unable to).

Short Form 36 (SF-36)

The SF-36 is a multi-purpose health survey with 36 questions and very popular instrument for evaluating health-related quality of life (QoL). The questionnaire measures functional health and well-being from the patient's point of view. The 35 questionnaire are aggregated into eight multi-item health domains: physical functioning (PF), role physical (RP), bodily pain (BP), general health (GH), vitality (VT), social functioning (SF), role emotional (RE), and mental health (MH) (based on classification shown in [Table 3](#)). The 8 domains, in turn, can be aggregated into two summary domains tapping physical and mental health: a physical component summary (PCS, including PF, RP, GH and BP) and a mental component summary (MCS, including MH, RE, SF, and VT). The SF-36 V2 health Survey form will be used for this study and the norm-based score for each domain will be calculated using Optum's SF36v2/SF-12v2 scoring software. Higher scores are associated with a better QOL. The change and percentage change from Baseline will be tabulated at the scheduled visits.

Table 3: The Abbreviated Item Content for the SF-36 Health Survey Domain Scales

Scale	Item	Abbreviated Item Content
Physical Functioning (PF)	3a	Vigorous activities, such as running, lifting heavy objects, or participating in strenuous sports
	3b	Moderate activities, such as moving a table, pushing a vacuum cleaner, bowling, or playing golf
	3c	Lifting or carrying groceries
	3d	Climbing several flights of stairs
	3e	Climbing one flight of stairs
	3f	Bending, kneeling, or stooping
	3g	Walking more than a mile
	3h	Walking several hundred yards
	3i	Walking one hundred yards
	3j	Bathing or dressing oneself
Role-Physical (RP)	4a	Cut down the amount of time one spent on work or other activities
	4b	Accomplished less than you would like
	4c	Limited in kind of work or other activities
	4d	Had difficulty performing work or other activities (e.g., it took extra effort)
Bodily Pain (BP)	7	Intensity of bodily pain
	8	Extent pain interfered with normal work
General Health (GH)	1	Is your health: excellent, very good, good, fair, poor
	11a	Seem to get sick a little easier than other people
	11b	As healthy as anybody I know
	11c	Expect my health to get worse
	11d	Health is excellent
Vitality (VT)	9a	Feel full of life
	9e	Have a lot of energy
	9g	Feel worn out
	9i	Feel tired
Social Functioning (SF)	6	Extent health problems interfered with normal social activities
	10	Frequency health problems interfered with social activities
Role-Emotional (RE)	5a	Cut down the amount of time spent on work or other activities
	5b	Accomplished less than you would like
	5c	Did work or other activities less carefully than usual
Mental Health (MH)	9b	Been very nervous
	9c	Felt so down in the dumps that nothing could cheer you up
	9d	Felt calm and peaceful
	9f	Felt downhearted and depressed
	9h	Been happy
Reported Health Transition (HT)	2	How health is now compared to 1 year ago

Ring Size Assessment

Per protocol, ring size is assessed using the study provided ring sizer widget and the fourth finger of the non-dominant hand. The ring size to record is the one with the tightest fit. If the finger is too large to be measured by the ring sizer then use the fifth finger (and make a note of this). The same finger will be used throughout the trial. The ring size circumference (mm) will be calculated as:

$$\text{ring size circumference} = \text{ring size} * 3.14159$$

Only subjects with post-treatment values using the identical finger as the one used for baseline value will be included in the change and percent change from Baseline analysis.

